6.12.2.2. Hypersensitivity, Immediate and Non-Immediate

Two main analyses are performed in support of assessment of potential immediate hypersensitivity, including anaphylaxis, and well as potential non-immediate hypersensitivity. These analyses will be conducted for the Summaries of Clinical Safety for the Induction and Maintenance Periods.

Time Period A, of potential immediate hypersensitivity, includes all TEAEs occurring on the day of study drug administration.

Time Period B, of potential non-immediate hypersensitivity, includes all TEAEs occurring strictly after the day of study drug administration (but prior to subsequent drug administration).

Analyses for both time periods use the current standardized Medical Dictionary for Regulatory Activities (MedDRA) queries (SMQs) to search for relevant events. TEAEs are characterized as follows:

- Anaphylactic reaction SMQ (20000021; narrow, algorithm per MSSO SMQ guide, and broad). Algorithm terms apply only for Time Period A.
- Hypersensitivity SMQ (20000214; narrow and broad)
- Angioedema SMQ (20000024; narrow and broad).

The number and percentage of patients who experienced a TEAE for the following will be analyzed for each of the 2 time periods:

- Any narrow or algorithmic term from any 1 of the 3 SMQs indicated above (that is, combined search across narrow and algorithmic portions of all 3 SMQs). Algorithm terms apply only for Time Period A.
- Any narrow scope term within each SMQ, separately (that is, narrow SMQ search)
- Any term within each SMQ, separately (that is, broad SMQ search).

Within query, individual PTs that satisfy the queries will be summarized.

The Anaphylactic reaction SMQ algorithm will be run only for Time Period A. The SMQ defines a category (A, B, C, D) for each SMQ PT. All Narrow terms have category A, and the occurrence of a Narrow term satisfies the algorithm. Additionally, a pair of PTs *from the same drug administration* satisfies the algorithm if the 2 events are from different categories (that is, B&C, or B&D, or C&D). Both contributing events must begin within Time Period A. Tables will summarize (the number of patients experiencing) each PT that contributes to such an algorithmic pair, and include such terms in the combined narrow and algorithmic search. Broad events that do not contribute to the algorithm will be summarized in a distinct portion of the table.

For Time Period A only, the number and percentage of each PT that is not in any of the 3 SMQs will be summarized overall and by individual PT. Only PTs that occur in at least 3 patients receiving LY3074828 will be displayed in this portion of the table.

The PT and LLT are listed for summary in decreasing order of incidence for LY-treated patients. Note that an individual patient may contribute multiple events. Also, a single event may satisfy multiple SMQ, in which case the event contributes to every applicable SMQ.

6.12.2.3. Injection Site Reactions

A summary will be provided for the Induction and Maintenance Periods, by treatment group, of the number of patients with reported events that map to any 1 of the following:

- MedDRA High Level Term (HLT) of Injection site reaction
- HLT of Administration site reaction.

The number and percentage of patients who experienced a TEAE for the following will be analyzed:

- Any term from either of the HLTs indicated above (that is, a combined query of these HLTs)
- Any term within each HLT separately.

Within HLT, individual PTs that satisfy the queries will be summarized.

The PT will be listed for summary with each category in decreasing order of incidence for LY-treated patients.

Injection site reactions occurring during the Rescue Period will be listed.

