PPD/QuantIFERON-TB Gold (per local guidelines)	X							Subjects will return 2 to 3 days after Visit 1 to have their PPD test read.
ECGs	X						X	This should be completed prior to any study dose administration or blood draw. Subjects should be supine for approximately 5 to 10 minutes before ECG collection and remain supine but awake during ECG collection.
C-SSRS	X	X	X	X	X	X	X	
CCI [REDACTED]		■	■	■	■	■	■	[REDACTED]
Study drug dosed		X			X		X	At Week 16, subjects will only receive study drug dosing if PASI <90.

Induction Dosing Period (Visits 1-7)								
Visit No.	V1	V2	V3	V4	V5	V6	V7	Comments
Week Relative to Study Drug Start	-4	0	2	4	8	12	16	All activities should be completed prior to any study dose administration unless otherwise stated below.
Day with Visit Tolerance Interval	≤28 from V2	0	14 ± 2	28 ± 3	56 ± 5	84 ± 5	112 ± 5	Visit 1 procedures may be conducted over more than 1 day as long as all tasks are completed within the allowable visit tolerance (at least 3 days should be allowed for receipt of laboratory test results).
Clinical Efficacy								
PASI	X	X	X	X	X	X	X	
sPGA	X	X	X	X	X	X	X	
PSSI, if applicable		X	X	X	X	X	X	Once a subject experiences symptoms related to scalp involvement, this form should be completed at all remaining indicated visits.
Whole body photographs		X					X	If subject has agreed to whole body photographs.
Health Outcomes								
PSS	Electronic Diary Taken Daily from Screening (V1) up to Week 16 (V7)						X	
PatGA		X	X	X	X	X	X	
DLQI		X	X	X	X	X	X	
SF-36		X					X	
Laboratory Tests								
Hematology	X	X	X	X	X	X	X	Unscheduled blood chemistry and hematology panels may be performed at the discretion of the investigator.
Lymphocyte subsets		X					X	
Serum chemistry	X	X	X	X	X	X	X	Unscheduled blood chemistry and hematology panels may be performed at the discretion of the investigator.
Urinalysis	X	X			X		X	

Induction Dosing Period (Visits 1-7)								
Visit No.	V1	V2	V3	V4	V5	V6	V7	Comments
Week Relative to Study Drug Start	-4	0	2	4	8	12	16	All activities should be completed prior to any study dose administration unless otherwise stated below.
Day with Visit Tolerance Interval	≤28 from V2	0	14 ± 2	28 ± 3	56 ± 5	84 ± 5	112 ± 5	Visit 1 procedures may be conducted over more than 1 day as long as all tasks are completed within the allowable visit tolerance (at least 3 days should be allowed for receipt of laboratory test results).
HBsAg, HBcAb, HBsAb	X							

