Vital signs (BP and heart rate), body temperature only if clinically indicated	X	X	X	X	X	X	X	X	X	X	X	Sitting blood pressure and pulse, to be obtained at approximately the same time as ECG measurements or blood sampling. When multiple assessments are scheduled for the same time point, the order of completion should be as follows: ECG, vital signs, and then blood sampling.
ECGs									X			ECGs should be performed before any blood is drawn. Subjects should be supine for approximately 5 to 10 minutes before ECG collection and remain supine but awake during ECG collection.
C-SSRS	X	X	X	X	X	X	X	X	X	X	X	
CCI												

Maintenance Dosing Period (Visits 8-18)												
Visit No.	V8	V9	V10	V11	V12	V13	V14	V15	V16	V17	V18	Comments
Week Relative to Study Drug Start	20	24	28	32	36	40	44	48	52	56	60	All activities should be completed prior to any study dose administration unless otherwise stated below.
Day with Visit Tolerance Interval	140 ± 5	168 ± 5	196 ± 5	224 ± 5	252 ± 5	280 ± 5	308 ± 5	336 ± 5	364 ± 5	392 ± 5	420 ± 5	
Study drug dosed	X	X	X	X	X	X	X	X	X	X	X	Subjects assigned to PRN will be evaluated at every visit to determine if dose needed. Subjects assigned to Q8W will get dosed on odd number visits.
Clinical Efficacy												
PASI	X	X	X	X	X	X	X	X	X	X	X	
sPGA	X	X	X	X	X	X	X	X	X	X	X	
PSSI, if applicable	X	X	X	X	X	X	X	X	X	X	X	Once a subject experiences symptoms related to scalp involvement, this form should be completed at all remaining indicated visits.
Whole body photographs				X					X			If subject has agreed to whole body photographs.
Health Outcomes												
PSS				X					X			
PatGA				X					X			
DLQI				X					X			In addition to the marked visits, DLQI also taken at PRN dosing or rescue treatment visits.
SF-36				X					X			
Laboratory Tests												
Hematology	X	X	X	X	X	X	X	X	X			Unscheduled blood chemistry and hematology panels may be performed at the discretion of the investigator.
Lymphocyte subsets									X			

Maintenance Dosing Period (Visits 8-18)												
Visit No.	V8	V9	V10	V11	V12	V13	V14	V15	V16	V17	V18	Comments
Week Relative to Study Drug Start	20	24	28	32	36	40	44	48	52	56	60	All activities should be completed prior to any study dose administration unless otherwise stated below.
Day with Visit Tolerance Interval	140 ± 5	168 ± 5	196 ± 5	224 ± 5	252 ± 5	280 ± 5	308 ± 5	336 ± 5	364 ± 5	392 ± 5	420 ± 5	

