5.1. Summary of Study Design

Study AMAF is a multicenter, randomized, parallel-arm, placebo-controlled trial with 4 study periods in subjects with moderate-to-severe plaque psoriasis.

[figure not shown]
Screening Period (≤4 weeks): Subjects will be evaluated for study eligibility ≤28 days before the baseline visit (Visit 2/Week 0). At the baseline visit (Visit 2), subjects who fulfill the eligibility criteria will be randomized to 1 of 4 induction treatment arms.

Induction Period (16 weeks): A double-blind, 16-week Induction Period is designed to establish the efficacy and safety of LY3074828 administered at Visit 2 (Week 0) and Visit 5 (Week 8). Subjects will be randomized to 1 of 4 induction treatment arms (LY3074828 30 mg SC, LY3074828 100 mg SC, LY3074828 300 mg SC, and placebo every 8 weeks [Q8W]) stratified on the basis of previous exposure to biologic therapy for treatment of psoriasis.

Maintenance Period (88 weeks): The Maintenance Period consists of 88 weeks of treatment. At the end of the Induction Period (Week 16), subjects will continue treatment in the Maintenance Period which is intended to explore 1 of 2 treatment strategies through Week 104. All placebo subjects and subjects assigned to treatment with LY3074828 who have a <90% improvement in Psoriasis Area and Severity Index (PASI) from baseline (PASI 90) at Week 16 will receive LY3074828 300 mg SC Q8W during the entire Maintenance Period. Subjects with ≥PASI 90 PRN dosing group) at Week 16 will only be dosed with LY3074828 at the baseline dose level assignment no more frequently than Q8W when disease activity level is <PASI 90, and this will continue until ≥PASI 90 is regained.

Follow-up Period (16 weeks): The Follow-up Period will include a visit every 4 weeks for a total of 16 weeks following Visit 29 to assess subject safety and study drug efficacy.

[Figure 5.1](#) illustrates the study design.

^a Visits will occur every 4 weeks in the Maintenance and Follow-up Periods.
 Abbreviations: PASI = Psoriasis Area and Severity Index; PRN = as needed; Q8W = every 8 weeks.

Figure 5.1. Illustration of study design for Clinical Protocol I6T-MC-AMAF.

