6.1.1. Subject Populations for Analyses

For purposes of analysis, populations for analyses are described in [Table 6.1](#).

Table 6.1. Subject Populations for Analyses

Population	Description
Intent-to-treat (ITT) (Induction Period Efficacy)	All randomized subjects, even if the subject does not take the assigned treatment, does not receive the correct treatment, or otherwise does not follow the protocol: 
 Unless otherwise noted, efficacy and health outcomes analyses for the Induction Period will be conducted on this population. Subjects will be analyzed according to the treatment to which they were assigned.
Induction Period Safety	All randomized subjects who received at least 1 dose of study treatment: 
 Unless otherwise noted, safety analyses for the Induction Period will be conducted on this population. Subjects will be analyzed according to the treatment to which they were assigned.
Maintenance Period Efficacy	All randomized subjects who have entered the Maintenance Period (see definition of entering Maintenance Period in Section 6.1.2.1): 
 Unless otherwise noted, efficacy, and health outcomes for the Maintenance Period will be conducted on this population. Subjects will be analyzed according to the treatment to which they were assigned in Maintenance Period.

Population	Description
Maintenance Period Safety	
All randomized subjects received at least 1 dose of study treatment who have entered the Maintenance Period (see definition of entering Maintenance Period in Section 6.1.2.1):
 
 • Unless otherwise noted, safety analyses for the Maintenance Period will be conducted on this population. • Subjects will be analyzed according to the treatment to which they were assigned in Maintenance Period, with all LY3074828 300 mg Q8W arms combined, that is, there will be 4 treatment groups in the Maintenance Period: 
 ○ LY 300 mg PRN ○ LY 100 mg PRN ○ LY 30 mg PRN ○ LY 300 mg Q8W (including subjects from 4 Induction Period treatment groups)

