6.1.2. Definitions

6.1.2.1. Study Time Intervals

Induction Period

All subjects who were randomized to the study are considered as entering the Induction Period.

The start of the Induction Period is defined as the date of first injection following randomization. For subjects who were randomized but not dosed, the Induction Period starts at the randomization date.

The end of the Induction Period is defined as the date of PASI measurement at Week 16, or the early termination date if subjects discontinued from study prior to or at Week 16, or Day 117, whichever comes first.

Maintenance Period

All subjects who had Week 16 visit with PASI measurement (except the ones discontinued the study at Week 16) are considered to have entered the Maintenance Period.

The start of the Maintenance Period is defined as the same date as end of the Induction Period, which is the date of PASI measurement at Week 16.

The end of the Maintenance Period is defined as the visit date at Week 104, or the date when the subjects received rescue treatment, or the early termination date if subjects discontinued from study prior to or at Week 104, whichever comes first.

Rescue Period

All subjects in PRN groups who received at least 1 dose of rescue treatment are considered to have entered the Rescue Period, and will be included in the Rescue Period analysis population.

The start of the Rescue Period is defined as the date the patient received the first dose of rescue treatment.

The end of the Rescue Period is defined as the visit date at Week 104, or early termination date if subjects discontinued from study prior to or at Week 104, whichever comes first.

Follow-up Period

All subjects who had Visit 29 are considered to have entered the Follow-up Period, and will be included in the Follow-up Period analysis population.

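### Maintenance injection-site and same-day reaction percentages count PRN subjects who receive no Maintenance injection, and no per-injection rate is planned

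*SAP*

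**What the plan says.** **Injection-site table.** SAP 6.12.2.3 states: "A summary will be provided for the Induction and Maintenance Periods, by treatment group, of the number of patients with reported events" that map to either of two MedDRA high-level terms. The statistic is the number and percentage of patients. No denominator specific to this table is given. Injection-site reactions during Rescue are only listed.

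**Hypersensitivity tables.** SAP 6.12.2.2 also covers Induction and Maintenance and also counts patients. Time Period A is the day of drug administration. Time Period B "includes all TEAEs occurring strictly after the day of study drug administration (but prior to subsequent drug administration").

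**Denominator.** SAP Table 6.1 defines the Maintenance Period Safety population as "All randomized subjects received at least 1 dose of study treatment who have entered the Maintenance Period". The dose may have been given at any time, Induction included. Entry is defined in SAP 6.1.2.1 by a visit, not by an injection: "All subjects who had Week 16 visit with PASI measurement (except the ones discontinued the study at Week 16) are considered to have entered" the period.

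**Dosing.** The Protocol Schedule of Activities says "At Week 16, subjects will only receive study drug dosing if PASI <90", so PRN subjects begin Maintenance without an injection. After that, under SAP 5.1, they "will only be dosed with LY3074828 at the baseline dose level assignment no more frequently than Q8W when disease activity level is <PASI 90". For the other group the Schedule says "Subjects assigned to Q8W will get dosed on odd number visits".

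**Related provisions.** SAP 6.12 rules out comparisons between Maintenance groups. SAP 6.12.1.2 reports total active injections by treatment group, and SAP 6.9.3 reports the number of PRN doses and the week of the first one. SAP 6.12.2.1 allows person-time-adjusted incidence rates, but only if dropout differs or an event needs further study.

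**The concern.** A reaction on the day of dosing cannot occur in someone who is not dosed, and a new injection-site reaction is not expected without an injection. Keeping never-injected subjects in the denominator lowers the PRN percentage for a reason unrelated to how well the injection is tolerated. The lower number of doses among PRN subjects who are retreated lowers it again. A reader who sets the PRN rows against the Q8W row could conclude that PRN injections are better tolerated when the risk per dose is the same.

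This matters because the protocol's design rationale (section 5.4) sets continuous dosing against PRN dosing, and SAP 5.2 says the PRN results will support the choice of maintenance strategy for Phase 3.

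Time Period B raises a separate labelling question. After a subject's last dose, the window has no maximum length within the period. An event many months after an injection can then be counted as a potential non-immediate hypersensitivity reaction. The SAP also does not say whether an Induction dose opens a window for events in Maintenance.

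**Working it through.** The documents state no reaction rate and no never-injected share, so there is no planned figure to reproduce on this point. The schedule is consistent: 104 − 16 = 88 weeks of Maintenance.

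**1. Doses possible in Maintenance**
- Q8W, odd-numbered visits from Visit 7 (Week 16) to Visit 29 (Week 104): Weeks 16, 24, …, 104 = 12 doses. It is 11 if the Week 104 dose falls outside the study; for subjects entering the extension, the Schedule of Activities leaves that dose to the extension protocol. Under SAP 6.12, Week 16 events count in Maintenance.
- PRN, earliest at Week 20 and at most every 8 weeks: Weeks 20, 28, …, 100 = 11 doses at most, and 0 if response is never lost.

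**2. Effect of the denominator**

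Tabulated % = (1 − f) × % among injected subjects. The share f is assumed.

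| f | 5% among injected | 10% among injected | 20% among injected |
|---|---|---|---|
| 0.1 | 4.5% | 9% | 18% |
| 0.3 | 3.5% | 7% | 14% |
| 0.5 | 2.5% | 5% | 10% |

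For scale, at the SAP's planning response rate an active arm sends 50 × 0.60 = 30 subjects to PRN. At f = 0.3 the injected number is 21, and at f = 0.5 it is 15.

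**3. Effect of unequal dose counts**

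Patient-level risk over k doses = 1 − (1 − p)^k. Assume p = 2% per dose in every arm and 3 doses in each retreated PRN subject.
- Q8W, 12 doses: 1 − 0.98^12 = 21.5% (11 doses: 19.9%).
- PRN, injected subjects only: 1 − 0.98^3 = 5.9%.
- PRN, all who entered: 5.9% × (1 − f).

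| f | PRN as tabulated | Gap to Q8W (12 doses) | Part due to denominator |
|---|---|---|---|
| 0.1 | 5.3% | 16.2 points | 0.6 points (4%) |
| 0.3 | 4.1% | 17.4 points | 1.8 points (10%) |
| 0.5 | 2.9% | 18.6 points | 2.9 points (16%) |

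Under these assumptions most of the gap comes from 12 against 3 doses. Changing the denominator alone would leave it in place. A rate per dosing visit, 2% in both groups here, removes it.

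**4. Time Period B**

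Suppose an Induction dose does open a window. Consecutive windows then cover the whole period except the dosing days. Maintenance runs 88 × 7 = 616 days, or 617 counting both ends.
- Q8W: 617 − 12 = 605 days. PRN with 3 doses: 614 days. PRN never re-dosed: 617 days.
- Background risk = 1 − exp(−rate × days / 365.25). At an assumed 0.10 events per patient-year this is 15.3% for Q8W (605 days) and 15.5% for PRN (614 or 617 days). The difference between 605 and 617 days is 0.28 points, and 0.15 to 0.47 points for rates of 0.05 to 0.20.
- The longest single window, from a Week 8 dose to Week 104, is 96 weeks, of which at most 88 lie in Maintenance.

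Suppose instead that only Maintenance doses open a window. Never-injected PRN subjects then have none. If injected PRN subjects have a window covering half the period (308 days, assumed), the PRN percentage at 0.10 events per patient-year is 8.1% × (1 − f) = 7.3%, 5.7% or 4.0% at f = 0.1, 0.3 or 0.5, against 15.3% on Q8W. The choice the SAP leaves open is therefore consequential.

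**The case against.** **The table answers a legitimate question.** A percentage by assigned regimen shows how many patients on that strategy have a reaction, and fewer reactions through fewer injections is a real consequence of PRN dosing. This stands, and it is why the planned percentage should stay.

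**No comparison is planned, and none would be clean.** SAP 6.12 rules out Maintenance comparisons. The groups are formed by Week 16 response, and two of the three PRN arms also differ from Q8W in dose. This stands and limits the importance of the point. It does not stop the rows being read against each other.

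**Dose counts are reported elsewhere.** Total injections and PRN dose counts let a reader see the imbalance. They do not show how many injected subjects reacted, and because a dose may take up to four injections (Protocol 7.1), an injection total need not equal dosing visits. The person-time rates are conditional and do not adjust for injections, since PRN and Q8W subjects can have similar follow-up with very different dose counts.

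**Stronger readings are tempting but not supported.** A reader might infer that the non-immediate window never ends. It closes at the next administration, and the Maintenance table is bounded by the end of the period. A reader might also infer that long PRN windows inflate PRN delayed-reaction percentages relative to Q8W, so that the tables mislead in both directions. The statistic counts patients, and the back-to-back Q8W windows cover nearly the same follow-up (step 4), so no material inflation appears. Finally, it would be wrong to attribute the whole PRN–Q8W gap to the denominator (step 3).

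**Conclusion.** The point holds for the Maintenance injection-site and Time Period A tables. The default denominator includes PRN subjects with no injection in the period, so PRN percentages understate risk among injected subjects by the factor (1 − f). With f assumed at 0.1 to 0.5, a true 10% shows as 9% to 5%. Unequal dose counts, 0 to 11 against 11 to 12, account for most of any remaining gap to Q8W, and nothing planned corrects for them. The actual size depends on f and on the risk per dose, and the documents give neither.

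For Time Period B the supportable point is narrower. The SAP should say whether Induction doses open a Maintenance window, and late events should be distinguishable from early ones. Because the tables are descriptive and the groups are not randomised, this is a worthwhile clarification rather than a threat to the trial's conclusions.

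**What to change.** In SAP 6.12.2.2 (Time Period A) and 6.12.2.3, for Maintenance:

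1. State the denominator and keep the planned percentage by assigned regimen.
2. Add beside it, by arm, (a) the number and percentage among subjects with at least one injection in the Maintenance Period and (b) events per 100 dosing visits.

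In SAP 6.12.2.2, for Time Period B:

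3. State whether a dose given in Induction opens a window for Maintenance events.
4. Show events by time since last dose, for example within one planned 8-week interval and later. This should be a supplementary split rather than a cut-off, because no figure in the documents establishes 8 weeks as the limit for a delayed reaction.

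The cost is SAP wording, a little programming and an extra row or two per table. Dose times are already recorded in the eCRF (Protocol 7.2.1), so no new data are needed. The additions do not make PRN and Q8W a randomised contrast, and a footnote should say so.
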